3. ABSTRACT

Strategies to prevent mother-to-child transmission (PMTCT) of HIV can reduce the risk of vertical transmission to less than 2%, but difficulties in adhering to the three pillars of PMTCT (maternal ART; exclusive breastfeeding; provision of ART prophylaxis to infant) has led to high rates of MTCT in sub-Saharan Africa and suboptimal maternal and infant health. The goals of the proposed research are to: 1) gain an understanding of the influences and mechanisms by which food insecurity (FI) and perinatal depression- two modifiable determinants of non-adherence to HIV treatment and exclusive breastfeeding- interact to impact adherence through a qualitative approach, and 2) Develop and pilot test a theory-based intervention that bolsters adherence to the PMTCT guidelines.

Methods: To better understand the relationship of food insecurity and depression among pregnant and postpartum women living with HIV we will use a longitudinal qualitative design. Thirty pregnant women will be recruited in their third trimester to participate in an in-depth interview. Each participant will be followed up to 12 months postpartum and asked to participate in three additional interviews in order to understand how depression changes over time (each participant will participate in a total of 4 interviews over this timeframe). Drawing upon findings from the in-depth interviews, in conjunction with key informant interviews (n= 5-up to 12) and focus group discussions with our target population (1-2 discussions with n=8-12 participants), we will apply the theoretical model of transitions theory to develop a multi-level intervention that improves adherence to PMTCT guidelines. We will test intervention acceptability and feasibility among 40 pregnant women (20 intervention and 20 current standard of care) and conduct follow-up to evaluate results at 6-months postpartum. **Candidate and Mentoring:** This project is being supported by an NIH K23 Career Development Award. I am a nurse-scientist with a background in health behavior change theory and infant feeding in the context of HIV. My mentor team is composed of exceptional research scientists from multiple disciplines with extensive experience in HIV treatment and prevention research in Kenya.

4. INTRODUCTION/BACKGROUND

In 2016, 160,000 children acquired HIV from mother to child transmission of HIV; 90% of these occurred in sub-Saharan Africa (SSA), including Kenya¹. PMTCT is now entirely possible through the efficacious strategies in Option B+ which include:²⁻⁶ 1) women with HIV be placed on lifelong antiretroviral therapy (ART), 2) women are advised to exclusively breastfeed (EBF) their infant for the first 6 months of life, and 3) provision of prophylactic HIV treatment to the HIV-exposed infant throughout the breastfeeding period. However, suboptimal engagement in care and inadequate ART adherence during pregnancy and, especially postpartum remain major concerns and compromise the ability for women to remain adherent to lifelong ART^{5,7-9}. On average, 50%, with some studies finding as high as 81% of HIV+ mothers^{10,11} are disengaged in care by 6 months postpartum, suggesting non-adherence to Option B+^{12,13}. As such, although adhering to PMTCT Option B+ reduces the risk of MTCT of HIV from 45% to less than 2%¹⁴, HIV incidence among children born to mothers living with HIV remains unacceptably high¹¹. For instance, in Kenya, MTCT rates are approximately 14%¹⁵. Furthermore, non-adherence to Option B+ increases morbidity and mortality for mothers¹⁶ and their infants¹⁷ and prevents both mothers and infants from the health and nutritional benefits of EBF¹⁸⁻²⁰. **In effect, we have solved PMTCT efficacy. We have not solved Option B+ implementation effectiveness and furthering maternal and child health for HIV+ mothers. In order to fully realize the benefits of Option B+ and fill a crucial knowledge gap, it is necessary to identify and address drivers of Option B+ non-adherence²¹.**

Two potential drivers of non-adherence to Option B+, that are also substantial health issues in SSA, including in Kenya, are food insecurity (FI) and perinatal (pregnancy and postpartum) depression. In SSA, over half of people living with HIV are moderately or severely food insecure²² and rates of depression among all pregnant and postpartum women range from 10-47%²³. FI is inextricably linked with poor health outcomes among people living with HIV, including increased disease progression, lower ART adherence^{24,25}, and higher mortality²⁶. Perinatal women are uniquely vulnerable to FI due to nutrient demands being higher, the effort required to prepare food, and financial constraints related to being obliged to leave the workforce²⁷. FI during pregnancy is associated with poor pregnancy outcomes, including low birth weight and gestational diabetes^{28,29}, and increased risk of MTCT²⁵. Postpartum FI can impact breastfeeding outcomes³⁰, child cognitive development³¹ and increase the risk of MTCT of HIV³².

In separate studies among women living with HIV, depression has been associated with poor adherence to ART^{17,33-37} and EBF practice³⁸⁻⁴⁰, as well as the risk of MTCT of HIV^{41,42}. FI is an important driver of depression^{27,43}. A cross-sectional study found that FI was associated with maternal depression among all women across four ethnic groups in Tanzania⁴⁴. The authors proposed several explanations; FI can lead to poor diet exacerbating anxiety and depression; FI can lead to feelings of disempowerment increasing depression; and both FI and depression share roots in larger inequalities preventing women from economic opportunities⁴⁴. These data show FI and depression are interrelated and burden perinatal women⁴⁵.

Interventions to improve Option B+ adherence by targeting FI and perinatal depression simultaneously have the potential for greater success, but are lacking^{4,13,46-49}. Existing interventions to improve PMTCT have focused almost exclusively on supporting adherence to one of the three pillars. In Kenya, Drake et al., applied a novel mHealth strategy to improve postpartum adherence to ART⁴⁶. Fayorsey et al., utilized a combination of support strategies including, phone and messaging, counseling and follow up support in the case of missed-appointments⁵⁰ to increase retention in care and adherence. Other interventions have focused on the EBF pillar of the PMTCT cascade^{51,52} through peer counselors⁵³ or clinic-based counseling sessions⁵⁴. Interventions to improve PMTCT must account for the multiple levels of influence that facilitate or inhibit HIV treatment and EBF success throughout pregnancy and postpartum, yet few do.

83 **5. JUSTIFICATION FOR THE STUDY**

84 **Current Research Gaps:** Although existing literature provides evidence linking FI and perinatal depression
85 among HIV+ women, there is a crucial gap in understanding the detrimental synergy in the interplay between these
86 two factors and their combined impact on Option B+ adherence^{27,55,61,62}. In addition, understanding maternal
87 retention to Option B+ adherence beyond 6-weeks postpartum is extremely limited⁴⁹. A sharp drop-off in
88 engagement of mothers and their infants occurs after 6 weeks, yet the reasons for this are unclear. This
89 compromises Option B+ adherence and long-term health as women fail to return for ART refills, infant HIV testing, or
90 infant feeding follow-up. Longitudinal data are needed to help understand this trend. Moreover, theory-based
91 approaches to mitigate non-adherence among postpartum HIV+ women are lacking⁶⁶ and none have focused on
92 addressing FI and depression together.

93 Findings from phase one of our study demonstrated that financial insecurity during the perinatal period was
94 detrimental to the mental health and food security of mothers living with HIV,⁸² and cash transfers have been shown
95 to improve outcomes for low-income families in Kenya.^{83,84} Yet, little is known about the specific benefits of cash
96 transfers to perinatal women living with HIV (WLWH) and their infants in this setting. In addition, participants from
97 phase one also reported challenges, including significant stress, related to safe infant feeding, a key component of
98 the prevention of mother to child transmission strategy. Barriers to current infant feeding guidelines (specifically EBF
99 for the first 6-months postpartum) are now well documented,⁸⁵⁻⁹⁰ however, more research is needed to develop and
100 test interventions that support women to overcome these barriers.

101

102

103

104

105

6. HYPOTHESIS

106

Hypothesis 1: We hypothesize that higher levels of food insecurity and depression lead to lower adherence to prevention of mother to child transmission of HIV strategies. These strategies include HIV treatment for the mother, treatment for her infant and to exclusively breastfeed for 6 months.

109

Hypothesis 2: We hypothesize that targeted support provided to women living with HIV during the transition period from pregnancy to postpartum can improve adherence to the prevention of mother to child transmission of HIV guidelines.

112

113

6b. Theoretical framework Under the mentorship of [name], we developed a conceptual framework to serve as a basis for the research proposed here. This framework draws from Weiser et al.'s framework illustrating the relationship between FI and HIV/AIDS outcomes. The original framework posits that FI and HIV/AIDS are linked in a harmful cycle through nutritional, mental health and behavioral pathways among people living with HIV⁶³. In this proposal, we apply these underpinnings to the complex relationship between FI and depression during the perinatal period and its impact on both PMTCT outcomes and maternal and infant health (Figure 1). Our framework draws on Syndemic Theory⁶⁴, the co-occurring conditions of poverty, depression and HIV resulting in a synergistic response worsening the effects of each state. As can be seen in Figure 1, I hypothesize that FI operates at the household level to impact perinatal depression. In turn, perinatal depression acts through several mechanisms, including perinatal stress, lack of self-efficacy and lack of social support to influence adherence to PMTCT strategies and maternal and infant health. Moreover, our model stresses that both FI and perinatal depression operate independently and jointly to impact maternal health. Previous work has demonstrated the link between stress, self-efficacy and social support and poor maternal outcomes postpartum⁶⁵⁻⁶⁷, however the role and the interplay of FI and perinatal depression among HIV+ women over time remains a knowledge gap we hope this proposal will start to fill.

120

121

122

123

124

125

126

127

128

129

[figure not shown]

Figure 1: Conceptual framework for food insecurity, depression and PMTCT linkages

In addition to the conceptual framework we have developed, Transitions Theory provides an innovative framework to explore HIV treatment adherence among pregnant and postpartum women.⁷⁵ The theory was developed by [name] who recognized healthy and unhealthy patterns in the way people experience and respond to different life transitions.⁷⁶ According to the theory, transitions occur over a period of time, they are characterized by change and adaptation and, once complete, result in a state of greater stability relative to the period of transition during which established support systems and resources may have been disrupted.⁷⁷ We will apply transitions theory³⁵ (making this the first study to apply a targeted theory to understand the experiences of postpartum women living with HIV) with the aim of improving PMTCT adherence. Our intervention development will adapt the Transition's Theory framework to target the specific personal, community, and societal issues identified by participants in the in-depth interviews.

7a. GENERAL OBJECTIVES

The proposed study will investigate the role of food insecurity and depression among women living with HIV and its impact on adherence to HIV treatment and prevention strategies as well as develop and test the acceptability and feasibility of a multi-level FI and depression intervention for perinatal HIV+ women in Kenya.

7b. SPECIFIC OBJECTIVES

- 1. Phase One: Identify factors that increase risk for or protect against FI and perinatal depression among HIV+ women in the Nyanza Region of Kenya** We will use qualitative techniques to clarify the protective factors, perceived causes, cultural understandings and individual perspectives of FI and perinatal depression by conducting a longitudinal design with in-depth interviews at 4 consequential time-points (i.e., prenatal, 1, 4 and after 6-months postpartum) with 30 HIV+ women who screen positive for depressive symptoms during routine care visits in Kisumu, Kenya. Our sample size is based on previous qualitative work where data saturation was reached with less than 30 participants. Applying grounded theory analysis techniques, I will describe how the above factors and perspectives of FI and depression are manifested in the perinatal period.
- 2. Phase Two: Apply findings from Phase One, using the theoretical framework of Transitions Theory to develop and test the acceptability and feasibility of a multi-level intervention to promote adherence to PMTCT strategies for perinatal HIV+ women in Kenya.** Drawing upon findings from Phase One of our study, in conjunction with consultation with key informant interviews with FACES clinic staff (n=5-12) and focus group discussions with our target population (1-2 discussion with n=8-12 participants per group), we will apply the theoretical model of transitions theory to develop a multi-level intervention that improves adherence to PMTCT guidelines. The intervention will be tested among 40 pregnant women (20 intervention and 20 current standard of care) and follow-up to evaluate results will occur at 6-months postpartum. The intervention will likely include individual mental health and nutrition counseling, and food support with or without some livelihood training.

In Phase One of our study, we identified perceived or actual milk insufficiency, as primary barrier to exclusive breastfeeding not addressed through the current education and support being provided at the clinic. Furthermore, we identified financial insecurity as a deeply-rooted threat to the health and well-being of perinatal WLWH and their infants across time. Based on our findings from our longitudinal qualitative study, our key informant interviews, focus groups with our target population and a review of the literature, we developed an intervention which we will pilot test to determine the potential impact of providing individualized support from a local lactation specialist along with monthly unconditional cash transfers (UCTs) to WLWH from 20-35 weeks pregnancy to 6-months postpartum.

The pilot test will be carried out among 40 pregnant women divided into 2 groups (n=20 intervention group, n=20 control group). The intervention group will receive personalized lactation support and monthly UCTs from approximately 30 weeks pregnancy to approximately 6-months postpartum. Personalized lactation support will be provided by a local, experienced lactation consultant. Her support will be aimed at providing person centered care to assess for and address barriers to optimal, safe infant feeding with a focus on exclusive breastfeeding for the first 6-months postpartum. The cash transfer will be 10,000 Kenyan shillings per month. This amount is slightly less than the median amount women in our preliminary study reported needing to meet their basic needs (13,500KES) and is in line with other cash transfers completed in the area.⁸³ It is equivalent to approximately 3.33USD per day, or about 40% more than the World Bank's most recent poverty line estimated of 1.90 USD per person per day. This amount is lower than the estimated median

182 monthly income for those informally employed in sectors such as retail trade or food service in Kenya
183 (estimated at 15,000 and 30,000KES monthly in rural and urban areas respectively).⁹¹ We expect this amount
184 will allow women to meet many of their household's basic needs during late pregnancy and throughout the
185 period of EBF when women are largely unable to maintain gainful employment.

186 The control group will receive the current standard care.
187

188 We will recruit women during their 20th-35th week of pregnancy and follow them until 6-months postpartum.
189 We will collect survey and clinical data at baseline (20-35 weeks pregnancy, 2-weeks, 4-weeks, 6-weeks, 3-
190 months and 6-months). We will conduct qualitative interviews at the end of the intervention period with all 20
191 participants in the intervention group to evaluate the acceptability of the pilot intervention as well as to
192 better understand how UCTs were used and the perceived impact on financial security, food security, mental
193 health, relationships with primary partners and the ability to adhere to PMTCT strategies.
194

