(i) Inclusion criteria: a) 20-35 weeks pregnant, b) Living with HIV, c) currently prescribed ART.

332
333 (ii) **Exclusion criteria:** a) High-risk pregnancy for reasons other than HIV status (e.g., pregnancy complications, preeclampsia, gestational diabetes, preterm labor), b) Self-reported participation in another ART adherence-related intervention study, c) Unable to understand consent process, and d) Planning on relocating out of Nyanza province in the following 12 months.

334 (c) **Sampling**

335 (i) **Sample size determination:** Sample size determinations are based on standardized feasibility procedures outlined in the literature.⁷⁸⁻⁸⁰

336 (ii) **Sampling procedures:** We will recruit 40 pregnant women from 2 designated clinics. 20 women will be recruited from Lumumba sub-County Hospital to participate in our intervention. During the same period, 20 women will be recruited from Kisumu County Hospital to participate as our control group. We have opted to use an alternate clinic site for the control group not receiving cash transfers to avoid interactions between women receiving cash transfers and women not receiving cash. We will recruit in-person, with a clinic staff member positioned in the clinic waiting room. Interested women will be assessed for eligibility using a brief screening assessment administered by a female study staff member. For women who are eligible, the staff member will privately give a more complete description of the study, and if the individual is interested, the consent process will begin.

337 (d) **Procedures**

338 (i) **Description of the intervention pilot test:** To test feasibility, we will recruit and enroll N= 40 women, 20-35 weeks pregnant, 18-years and above, living with HIV (n=20 for the intervention group and n=20 for the control group).

339 **Intervention group (n=20):** Women in the intervention group will receive personalized support for breastfeeding provided by a local skilled lactation specialist and a monthly UCT of 10,000KES.

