340 Women in this arm of the study will meet with a lactation consultant at 5 timepoints throughout the intervention: once during pregnancy and at 2-weeks, 4-weeks, 6-weeks and 3-months postpartum. During pregnancy, the lactation specialist will assess women's knowledge and experience with regards to breastfeeding and provide them information and support for optimal infant feeding after birth while emphasizing exclusive breastfeeding. Each post-partum visit with the lactation specialist will be individualized and continue to focus on optimizing infant feeding with a focus on exclusive breastfeeding for up to 6-months postpartum. During the postpartum sessions, the lactation specialist will assess for milk sufficiency or any other barriers to optimal infant feeding. The assessment will include the infant's weight and a physical assessment of women's breasts and breastfeeding practice. The lactation specialist will counsel women on how to address both perceived and actual milk insufficiency as well as address any of the other barriers to infant feeding as appropriate. Counseling topics will include women's breastfeeding timing and technique, diet, hydration and infant hunger and satiety cues to optimize safe infant feeding. Other treatments may include warm or cold compresses or the use of a breast pump to treat engorged breasts. The lactation specialist will not prescribe women any medications. Any medications the lactations specialist would recommend (for example an antibiotic to treat mastitis) will be recommended to the participant's primary perinatal care provider for further consideration and prescribing as appropriate. At the last visit (3-months postpartum) the lactation specialist will provide women with support and information about when and how to introduce affordable nutritious supplemental foods to their infants while at the same time promoting continued breastfeeding for 24-months or beyond.

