341 Women in the intervention group will also receive monthly UCT of 10,000KES sent directly to an MPESA accounts associated with their personal cell phone. Cash transfers using MPESA accounts have an electronic trail for auditing purposes and such transactions have already been successfully used in healthcare research in Kenya.⁹² If any interested and eligible participant does not have their own cellular phone with MPESA account, they will be provided with a low-cost phone for use during the study period. As a University of California San Francisco affiliated study, our research team will work together with the finance team at Global Programs Kenya to administer the UCT to participants.

342 **Control Group (n=20):** The women enrolled in the control arm will receive standard care. After the last data collection for the control group is complete (at around 6-months postpartum), control group participants will be offered a one-on-one informational session, designed by a lactation specialist, and provided by the same RA who administered the electronic surveys throughout the study period. The session will provide women with support and information about how to introduce affordable, nutritious supplemental foods to their infants while at the same time promoting continued breastfeeding for 24-months or beyond. The session will last 20-40 minutes, depending on the number of questions participants have.

387
388 **(ii) Description of the type of data to be collected and collection procedures:** Participants in both the intervention
389 and control groups will be asked to complete electronic surveys via tablet at baseline (20-35 weeks pregnant), 2-
390 weeks, 4-weeks, 6-weeks, 3-months and 6-months. The electronic surveys will collect information on a variety of
391 outcomes including socio-demographics, FI, financial stability, mental health, infant health, relationships, stigma,
392 empowerment, breastfeeding practices and adherence to HIV medications for participants and their infants (see
393 Table 3 for all topics and specific tools to be included in the survey). At each research encounter where the surveys
394 will be completed, infants will also be weighed by a trained member of our research team and clinic records will be
395 used to collect participant's viral loads, infants' HIV test results and information on health status and engagement in

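### Do the loosely worded start and end of the intervention, and a wrong poverty-line percentage, undermine the pilot?

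*Protocol*

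**What the plan says.** Section 7b (Specific Objectives, Phase Two) describes the timing of the intervention twice. The first description has individual lactation support along with "monthly unconditional cash transfers (UCTs) to WLWH from 20-35 weeks pregnancy to 6-months postpartum". The next paragraph has "personalized lactation support and monthly UCTs from approximately 30 weeks pregnancy to approximately 6-months postpartum". The same section sets recruitment: "We will recruit women during their 20th-35th week of pregnancy and follow them until 6-months postpartum". The inclusion criteria in section 8 (Intervention Pilot Test) agree with that window: "a) 20-35 weeks pregnant, b) Living with HIV, c) currently prescribed ART".

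The detailed procedure in section 8 sets five meetings with the lactation specialist: "once during pregnancy and at 2-weeks, 4-weeks, 6-weeks and 3-months postpartum". It then names the final one: "At the last visit (3-months postpartum) the lactation specialist will provide women with support and information". On cash it says: "Women in the intervention group will also receive monthly UCT of 10,000KES sent directly to an MPESA accounts". That paragraph gives no start date and no number of payments.

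Section 7b supports the amount with several comparisons. One of them reads: "It is equivalent to approximately 3.33USD per day, or about 40% more than the World" Bank poverty line of 1.90 USD per person per day.

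**The concern.** Read literally, the protocol has two start points. Under one, a woman enrolled at 20 weeks is paid straight away. Under the other, she waits about ten weeks. A woman enrolled at 31 to 35 weeks could not start at 30 at all. Lactation support likewise seems to have two end points, six months in the objectives and three months in the visit schedule.

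A pilot of feasibility and acceptability needs to know what was meant to be delivered. If the planned number of payments or sessions were open, the delivered number could not be called complete or incomplete. The time from the baseline survey, taken at recruitment, to the first payment would also be undefined. The poverty-line percentage does not follow from the two figures printed beside it, which raises the question whether the transfer amount was derived wrongly.

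**Working it through.** **Poverty line.** Inputs: 10,000 KES a month, 3.33 USD a day and 1.90 USD a day (section 7b); 800 KES equated with about 8 USD, that is 100 KES per USD (section 11, potential benefits).

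- The daily figure reproduces: 10,000 / 30 / 100 = 3.33 USD.
- The stated 40% does not: 3.33 / 1.90 - 1 = 0.753, about 75%.
- The nearest match uses the wrong denominator: 1 - 1.90 / 3.33 = 0.429, so the line is about 43% below the transfer.
- A true 40% excess would need 1.90 x 1.40 = 2.66 USD a day, or about 125 KES per USD (10,000 / 30 / 2.66). The protocol gives no such rate.

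The amount itself is stated directly in KES and is also set against the 13,500 KES that women in the preliminary study reported needing, other local transfers, and informal-sector income. Nothing is computed from the percentage.

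**Cash start.** Assume birth at 40 weeks, a month of 30.44 days and payments to six months postpartum. Payments = (40 - start week) x 7 / 30.44 + 6.

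| Start week | Payments |
|---|---|
| 20 | 4.60 + 6 = 10.60 |
| 30 | 2.30 + 6 = 8.30 |
| 35 | 1.15 + 6 = 7.15 |

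- If payment were withheld until week 30, a woman enrolled at 20 weeks would lose 10 x 7 / 30.44 = 2.30 payments, about 23,000 KES. The birth week cancels out of this difference.
- Suppose enrolment were also uniform over 20-35 weeks, for which the protocol gives no support. The mean enrolment week is 27.5. The mean of the later of enrolment and week 30 is (2/3) x 30 + (1/3) x 32.5 = 30.83. The difference is 3.33 x 7 / 30.44 = 0.77 payments per woman, or about 153,000 KES over 20 women.
- If payment simply follows enrolment, the number still runs from 10.60 to 7.15, a spread of 3.45 payments. That comes from the recruitment window alone and exceeds the 2.30 at issue.

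**Side by side, start.** The first description in section 7b repeats the recruitment window. The second gives an approximate week that lies inside it. No sentence withholds payment until week 30, so the two descriptions need not conflict: 30 can be a rounded typical value.

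**Side by side, lactation.** The objectives cover cash and lactation support in one joint phrase running to six months. The procedure lists five dated contacts, the last at three months, and no text schedules a later one. The six months mentioned in the procedure is the breastfeeding goal being counselled. The planned count in the detailed text is therefore five.

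**Use in the analysis.** Section 9(b), Phase Two, looks at scores over time within each group and between groups at each timepoint. It relates no outcome to the number of payments or sessions, and it concedes that the sample may be too small for statistical significance. Both groups enrol in the same gestational window.

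**The case for a change.** The strongest case for a change is that the protocol, not an analysis plan, defines the intervention, and nowhere says that cash begins at enrolment. Thirty is not the midpoint of 20-35 (that is 27.5). Section 7b also speaks of needs in late pregnancy, which fits a start near week 30 better than one at week 20. Staff with a woman at 20 weeks would have to infer what to do. Cash to a vulnerable group is also something the protocol itself says needs care.

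Part of this stands. The start rule is not written down in the text shown, and the objectives and the visit schedule differ on how long lactation support lasts. What does not stand is the step to a damaged pilot. The payment and KES gaps need a withholding rule that no sentence contains, and the totals need an assumed enrolment pattern as well. Section 11 mentions a separate consent form for intervention participants. Consent pages are not available here, so it cannot be claimed that the schedule is stated nowhere. Delivery is recorded in any case: transfers leave an electronic trail, and the specialist writes a note after every session.

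**Conclusion.** The inconsistencies are genuine but minor, and they call for no change to the design, sample size, data collection or analysis. The two start descriptions are compatible if week 30 is an approximate value within the 20-35 week window. The 2.30-payment gap (about 23,000 KES) applies only to a woman enrolled at 20 weeks and only if payment were held back until week 30. The 153,000 KES total further assumes uniform enrolment. Neither should be read as an expected discrepancy. Five lactation sessions are listed, so delivery of that component has a reference count. The poverty-line figure should read about 75% by its own inputs, and no other number depends on it.

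The passages on the cash start and the lactation period must be reconciled by the sponsor, together with the percentage. That is aligning wording, and which schedule is intended is the sponsor's to say. This conclusion rests on the comparisons planned in section 9(b). It would need another look if an analysis by amount of intervention received were added.
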